An asthma exacerbation requiring the use of systemic corticosteroids (tablets, suspension, or injection) for ≥ 3 days **	Prior and Concomitant Medications page of eCRF, coded appropriately so that systemic corticosteroids can be identified	Not applicable
A hospitalization or emergency room visit because of an asthma exacerbation	Asthma exacerbation reported as SAE; in case SAE was not reported (ie, in case asthma exacerbation required only emergency room visit which consequently is not reported as SAE), the Investigator assessment in the eCRF of occurrence of an asthma related event is to be utilized as the source data	Not applicable

ICS = inhaled corticosteroid; SABA = short-acting beta agonist

- * This criterion may be met via 2 consecutive calendar days of assessments (ie, morning and evening diary entries for calendar date 1) plus morning and evening diary entries for the calendar date 2) or over a span of 3 consecutive calendar days (ie, evening diary entry for calendar date 1 and morning diary entry for calendar date 2 plus evening diary entry for calendar date 2 and morning diary entry for calendar date 3).
- ** In the case which use of systemic corticosteroids being administered for an asthma exacerbation is ongoing at the end of the study, the duration will be considered to be ≥ 3 days – as in clinical practice corticosteroid prescription including tapering usually last more than 3 days – and therefore the subject will be considered to have met this criterion for an asthma related event.
- ** Subjects being administered systemic corticosteroids for ≥ 3 days for a nonasthma event, will be considered to have met this criterion for an asthma related event, provided they have corresponding signs and symptoms of an asthma exacerbation. Also, subjects being administered a single dose of a longterm acting systemic corticosteroid (eg, dexamethasone) with a dose equivalent to a treatment of ≥ 3 days with other short to midterm systemic corticosteroids will be considered to have met this criterion for an asthma related event. Such cases will be confirmed by the sponsor as having met the criterion for an asthma related event or not.

In addition, an Investigator assessment of the occurrence of an asthma related event is recorded in the eCRF at each visit during the course of the study.

Time to first asthma related event will be measured in days as follows:

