6.2.6.1 Symptom Scores

The ASD is a 6item daily measure of asthma symptom severity that assesses 3 core categories of asthma symptoms: breathing symptoms (difficulty breathing; wheezing; shortness of breath), chest symptoms (chest tightness; chest pain), and cough. The ASD is intended for twice daily completion and comprises a morning diary (for completion upon waking and referring to asthma symptoms during the nighttime) and an evening diary (for completion before going to bed and referring to asthma symptoms during the day).

Subjects are required to rate the 6 symptoms at their worst during the respective timeframes using an 11-point numeric rating scale ranging from 0 ('None') to 10 ('As bad as you can imagine') [6].

Individual morning and evening ASD symptom scores for the 6 symptoms of difficulty breathing, wheezing, shortness of breath, chest tightness, chest pain, cough will be reported for each symptom as recorded in the diary. If the assessment of a particular symptom is missing for either the morning or evening diary, then that symptom's score for that diary timepoint will be missing.

Mean symptom scores will be calculated for each symptom as the mean of the available scores for the applicable symptom for each week, as follows:

$$\frac{\text{sum of available entries for the week, for each symptom}}{\text{number of available entries for the week, for each symptom}}$$

A mean ASD score will be calculated as the mean of all available symptom scores for each week, as follows:

$$\frac{\text{sum of available entries for the week, for all symptoms}}{\text{number of available entries for the week, for all symptoms}}$$

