6.2.6.2 Additional Endpoints from Diary Data

A peak flow meter measures how well the lungs are able to expel air. Subjects will measure peak flow daily on a device provided by the sponsor and record the results in their diary. The daily peak flow rate as well as the use of SABA, which will also be recorded in the diary, will be used to assess the occurrence of asthma related events (see [Section 6.2.1](#)).

Peak flow rate is recorded daily by the subject. Mean peak flow rate will be calculated as the mean of all available recordings for each week, as follows:

$$\frac{\text{sum of available entries for the week}}{\text{number of available entries for the week}}$$

The first week post-baseline will start with the recording in the diary on Day 1 and will end with the recording in the diary on Day 7 (ie, if there are no missing entries, a week will comprise 7 entries). If the Day 1 entry is utilized as baseline (see [Section 9.2](#), Definition 1 for mean peak flow rate), the Day 1 entry will not be part of the first week post-baseline (ie, in this case the first week post-baseline will start with the Day 2 diary recording and will end with the Day 7 diary recording). If a subject has > 3 missing entries in a week, then the mean score for that week will be missing. Mean values for all subsequent weeks will be defined similarly, with the same rule for handling missing entries. Baseline is defined in [Section 9.2](#) (Definition 1 for mean peak flow rate).

The number of times (number of puffs/inhalations) a SABA is used will be assessed by reviewing the diary maintained by the subject. The number of puffs/inhalations of SABA is entered by the subject in their diary twice daily, ie, the morning diary is used to record number of SABA puffs/inhalations during the nighttime and the evening diary is used to record number of SABA puffs/inhalations during the day. For analysis of the SABA use data, beginning with the day on which the diary is activated through the earlier of the end of study date or the diary deactivation date, all missing entries will be considered 0 for analysis. Daily sums of SABA puffs/inhalations will be calculated as the sum of the morning diary and evening diary entries for the same calendar date. Mean daily number of puffs/inhalations over weekly periods will be calculated from the daily sums, as follows:

$$\frac{\text{sum of daily sums for the week}}{\text{number of days the diary was available for the week}}$$

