9.2 Baseline and Related Changes Definition

In general and unless otherwise specified, baseline is defined as the last available assessment prior to the first dose of the study drug.

CFB is calculated as: $CFB = observed\ value - baseline\ value$

CFB% is calculated as: $CFB\% = \left(CFB / \text{baseline value} \right) \times 100$ (if the baseline value is 0, CFB% cannot be calculated)

Where unscheduled/repeat assessments are relevant and exist for any subject at a particular visit they will also be considered in the baseline definitions, provided they remain prior to the first dose of study drug.

Visit 1a (Day 7 [2 days]) with diary activation was added to the protocol Schedule of Assessments in Protocol Version 4.0 (Amendment 3), 05 May 2022. Therefore, subjects enrolled prior to this amendment did not have a diary activated until the day of randomization (ie, they will not have diary entries during the 7 days preceding Visit 2). A baseline value cannot be calculated for subjects with no diary entries before the day of randomization. To include such subjects in analyses, additional definitions of baseline have been included in which Day 1 entries or Day 1 through Day 7 entries may be used for calculation of baseline when a subject does not have sufficient diary entries prior to Day 1. This approach has been taken given that all subjects have received a 30day regimen of stable asthma medications leading up to Day 1 which will be maintained until Day 14 per protocol; therefore, a Day 1 (or Day 1 through Day 7) diary entry is a reasonable representation of their baseline. The baseline definitions are detailed below for each of the following subject diary assessments:

Asthma Symptom Diary Assessment	Baseline Definition

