	
 Subjects whose diary was activated no later than Day -1, will have their baseline value calculated as: $\frac{\text{sum of daily sums from Day -7 through Day -1}}{\text{number of days the diary was available from Day -7 through Day -1}}$ Subjects for whom their diary was not activated by Day -1 but for whom the diary was activated on Day 1 and ≥ 1 Day 1 entry is available, will have their baseline value calculated as: $\frac{\text{sum of entries on Day 1}}{\text{number of days the diary was available from Day 1 through Day 1}}$ Subjects for whom their diary was not activated by Day 1, will have a null baseline.
	Definition 2:
	
 Subjects whose diary was activated no later than Day -1, will have their baseline value calculated as defined in Definition 1 above. Subjects for whom their diary was not activated by Day -1 but for whom the diary was activated for ≥ 1 day between Day 1 and Day 7, will have their baseline value calculated as: $\frac{\text{sum of daily sums from Day 1 through Day 7}}{\text{number of days the diary was available from Day 1 through Day 7}}$ Subjects for whom their diary was not activated by Day 7, will have a null baseline.
	Definition 3:
	
 Subjects whose diary was activated no later than Day -1, will have their baseline value calculated as defined in Definition 1 above. Subjects for whom their diary was not activated by Day -1, will have a null baseline.
	Definition 4:
	
 Subjects whose diary was activated no later than Day -4, will have their baseline value calculated as defined in Definition 1 above. Subjects for whom their diary was not activated by Day -4, will have a null baseline.
	Note: for the days the diary was available (ie, any day from diary activation through deactivation), all missing entries will be considered 0 for calculation of the baseline value
Mean peak flow rate	Baseline values will be calculated by the following 4 separate definitions. The primary baseline definition (Definition 1) will be used for all output that requires a comparison of peak flow rate to baseline. Definition 2 through 4 will only be used for the primary endpoint summary in the FAS and associated listings (ie, occurrence of an asthma related event; see Section 6.2.1).

Definition 1 (primary baseline definition):

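### The primary SABA baseline can rest on one half-day diary entry divided by a whole day, so a stable patient whose diary started on Day 1 may be counted as an event

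*SAP*

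**What the plan says.** Puffs are entered twice a day. SAP 6.2.6.2 states that "the morning diary is used to record number of SABA puffs/inhalations during the nighttime"; the evening diary covers the day. SAP 6.2.6.1 describes "a morning diary (for completion upon waking and referring to asthma symptoms during the nighttime".

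SAP 9.2 explains that the pre-baseline diary week came in with Amendment 3, so "subjects enrolled prior to this amendment did not have a diary activated until the day of randomization". For these subjects Definition 1 applies where "the diary was activated on Day 1 and ≥ 1 Day 1 entry is available, will have their baseline value calculated as" the sum of the Day 1 entries over the "number of days the diary was available from Day 1 through Day 1". That divisor is 1. The note to the table counts as available "any day from diary activation through deactivation", and "all missing entries will be considered 0 for calculation of the baseline value".

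After baseline, SAP 6.2.1 asks for at least 6 puffs above baseline per 24 hours on 2 consecutive days. A 24-hour period is either one calendar date (morning plus evening) or "evening diary entry for calendar date 1 and morning diary entry for calendar date 2".

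Definition 1 is the only SABA baseline for the Per Protocol repeat (SAP 10.6.1), for the Kaplan-Meier, log-rank and weekly SABA summaries (10.6.2), and for the under-150 eosinophil and 28-day repeats (10.6.3). Definitions 2 to 4 enter only as repeats of the primary endpoint summary in the Full Analysis Set.

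**The concern.** A diary switched on at the randomization visit was probably not in the subject's hands on waking that morning. Day 1 would then contain an evening entry and nothing else, even in a fully compliant subject. The numerator covers the day, the divisor counts a whole day, and the result is compared with sums that include the night.

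Scoring the blank as missing would not by itself repair this, because the divisor counts days and not entries. The symptom scores in the same SAP table are better protected: they need at least one morning and one evening entry, and they divide by the number of entries.

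A baseline that is too low makes unchanged patients look worse. The rule is the same in both arms, so false events are expected in both, and the treatment difference is diluted. The weekly change in SABA use also gains a spurious rise.

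**Working it through.** **The plan's own figure.** SAP 6.1.1 claims over 95% power with 40 per arm at 44% v 6% and 5% type I error (taken as two-sided).

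Power = Φ{[|p1 − p2| − 1.96 √(2p̄(1 − p̄)/n)] / √[(p1(1 − p1) + p2(1 − p2))/n]}

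With p̄ = 0.25 and n = 40 this is Φ{[0.38 − 1.96 × 0.0968]/0.0870} = Φ(2.19) = 98.6%. Exact enumeration of the Wald test gives 99.1% without and 98.2% with continuity correction. The claim is reproduced.

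**Size of the understatement.** Let n be the night share of use and k the number of calendar days the diary was available for baseline, the first holding only an evening entry. The baseline is too low by n/k. The documents do not give the night share; 30% to 50% is assumed.

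- k = 1 (activation on Day 1): 30% to 50%
- k = 4: 7.5% to 12.5%
- k = 7: 4.3% to 7.1%

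**No day-to-day variation.** The rise needed for an event falls from 6 puffs to 6 minus the usual night-time puffs. A constant user of 6 by night and 6 by day has baseline 6/1 = 6; each later 24 hours totals 12, a rise of 6, so the criterion is met with no change. At 4 + 4 the apparent rise is 4 and there is no event. Without variation, only subjects with at least 6 night-time puffs are converted.

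**With variation.** Assumptions: stable subjects, Poisson half-day counts, 98 days, both 24-hour alignments, Day 1 excluded from the event window where it serves as baseline, 20,000 simulated subjects per setting. Probability of a false SABA event:

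| Puffs/day | Night share | Day 1 evening only | One full 24 h | 7-day mean |
|---|---|---|---|---|
| 2 | 50% | 1.7% | 0.7% | 0.0% |
| 4 | 30% | 30% | 15% | 1.4% |
| 4 | 50% | 46% | 14% | 1.5% |
| 6 | 30% | 56% | 29% | 8% |
| 6 | 50% | 78% | 29% | 8% |

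Separate runs differ by a point or two. The half-day effect is the step from the fourth column to the third. The step from the fifth to the fourth is the price of a single-day baseline. With overdispersed counts (negative binomial, 4 puffs/day, equal split) the three rates are 70%, 38% and 16%: the order is the same, and all are higher.

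**Effect on the comparison.** If a share s of subjects is affected and each has false-event probability f, put g = s × f. Each arm's rate p becomes p + g(1 − p), and the difference shrinks by the factor 1 − g. Assume s = 20% at 4 puffs/day, equal split.

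- Half-day: g = 0.20 × 0.465 = 0.093. Rates 0.44 + 0.093 × 0.56 = 0.492 and 0.06 + 0.093 × 0.94 = 0.147. Difference 34.5 points, power about 93%.
- One full 24 hours: g = 0.20 × 0.144 = 0.029. Rates 0.456 and 0.087. Difference 36.9 points, power about 97%.

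**The case against.** The strongest objection is that no text says the Day 1 morning entry is absent, and some text points the other way. The symptom-score fallback in SAP 9.2 needs a morning and an evening entry between Day -7 and Day 1. A subject activated on Day 1 can satisfy it only with a Day 1 morning entry, so the authors seem to have expected one. Peak flow was at first collected on the morning page (SAP 6.2.1), and the current protocol's Table 1 notes time it from 10:00 AM to 2:00 PM and allow it in clinic on visit days. The morning page may therefore have been open at the visit. This stands as a limit: a late morning entry removes the problem for that subject. It does not rescue the rule, which accepts one entry either way.

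Second, the primary analysis is repeated under four definitions. For a Day 1 activation, Definition 2 averages Days 1 to 7, and Definitions 3 and 4 give a null baseline. A distortion could show up as disagreement between them. That is true, but Definition 1 stays primary and stays the only baseline for the other analyses listed above.

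Third, a reader might infer that every subject enrolled before Amendment 3 has a half-day baseline, that the whole gap between 46% and 1.5% comes from it, that diaries started at Visit 1a are seriously affected, or that the rule favours the drug. None of these is supported. The Day 1 entries are not described; much of that gap is the single-day effect; activation at about Day -7 costs only 4% to 7% of baseline, and none if the diary started earlier within the visit window; and the rule is the same in both arms.

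**Conclusion.** The point holds in a limited form. As written, Definition 1 gives a wrong daily baseline for any subject whose diary starts on Day 1 and who has only the evening entry. Stable moderate or heavy users can then become false primary events; users of about 2 puffs/day are hardly touched. The expected consequence is dilution and lost power.

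The size in this trial cannot be fixed from the documents, which give neither the number of Day 1 activations, nor SABA use at entry, nor the night share. The simulated rates rest on the stated Poisson and split assumptions, and the fall in power from about 97% to about 93% on an assumed 20% affected at 4 puffs/day. This is a should-fix: the rule is faulty and cheap to repair, but the evidence does not show that it endangers the trial's conclusion.

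**What to change.** First, check whether Day 1 morning entries exist for the subjects activated on Day 1. Then amend Definition 1 in SAP 9.2:

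- Compute the SABA baseline only from complete 24-hour periods (one morning and one evening entry, in either alignment that SAP 6.2.1 accepts), and divide by the number of complete periods.
- For diaries first activated on Day 1, average the complete periods from Day 1 through Day 7. This is the Definition 2 window with the partial activation day removed.
- State whether days used for baseline can also count toward an event.
- Keep the current Definition 1 as a sensitivity analysis.

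A single evening-plus-next-morning pair would also remove the half-day error, but it leaves a noisy one-day baseline: about 14% false events at 4 puffs/day and 29% at 6. The Definition 2 average, even with its partial first day, gives about 2% and 12% (Poisson, equal split).

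The cost is a paragraph of SAP text and a small programming change, with no new data. There are two drawbacks. Some post-dose days enter the fallback baseline; SAP 9.2 already argues that Day 1 through Day 7 can stand for baseline because background therapy does not change until Day 14. And blanks after baseline would still count as 0 while baseline needs complete periods, which tends to lower event counts and should be acknowledged.

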9.3 Handling of Partial Dates

Rules for imputation of missing or partial dates to enable background calculation/classification of AEs and prior/concomitant medication/procedures are presented in [Appendix 2](#).

Listings will display the dates as collected on the eCRF.

9.4 Interim Analysis

No interim analyses are applicable.

9.5 Pooling Strategy for Study Sites

Data from all subjects will be pooled across study sites.

9.6 Visit Windows / Unscheduled Visits

A schedule of assessments is included in [Table 2](#). Additional visit windowing, beyond the protocol-defined windows, will not be applied.

Unscheduled measurements will be classified as unscheduled visits at the site. Unscheduled visits will not be included in by-visit summaries or analysis, but will be included in summaries of PCI values and will also be considered when the baseline assessment and worst overall post-baseline values are defined.

10 STATISTICAL ANALYSIS METHODS

10.1 Subject Disposition

The following subject listings will be provided, using the analysis set indicated:

- Screen failures (all subjects)
- Randomized subjects (RAS)
- Subject completion/discontinuation information (RAS)
- Inclusion/exclusion of subjects from analysis sets (RAS)

Summary tables will be provided using the RAS/all subjects (as applicable), including the following information: number of subjects who completed the study, number of subjects who discontinued the study early (including reason for early discontinuation), number of subjects who completed study drug treatment, number of subjects who discontinued study drug treatment early (including reason for early discontinuation), and number of subjects in each analysis set. The number of subjects screened and number of screen failures (including reason for screen failures) will also be summarized for all subjects screened. These summaries will be presented by treatment group and overall.

10.2 Protocol Deviations

Reported protocol deviations will be categorized to a deviation category and will also be categorized as significant/not significant prior to unblinding of data.

All deviations will be included in a subject listing, using the RAS.

Significant deviations will be summarized by treatment group and overall, using counts and percentages by deviation category (as applicable) for the RAS. Subjects will only be counted once within each deviation category.

10.3 Demographics and Baseline Characteristics

The following demographic and baseline characteristics will be included in a subject listing, using the RAS:

- Age
- Sex
- If female, whether of childbearing potential
- Race
- Ethnicity
- Baseline height, body weight, and BMI
- Screening and Baseline eosinophil level
- Part of sputum subset of subjects

The demographic and baseline characteristics will be summarized by treatment group and overall using descriptive statistics, for the RAS (including screening eosinophil level [< 150 eosinophils/ μ L, ≥ 150 eosinophils/ μ L] and sputum subset [Yes, No] as categorical variables).

BMI will be derived as:

$$BMI = \frac{\text{baseline weight (kg)}}{[\text{baseline height (m)}]^2}$$

10.3.1 Medical History

Medical history terms will be coded using MedDRA, version 24, 01 Sep 2021.

Medical history items will be included in a subject listing, using the RAS.

The number and percentage of subjects reporting any medical history will be summarized by SOC and PT, by treatment group and overall, for the RAS. A subject with multiple medical conditions will be counted once per SOC and PT. For computing percentages, the denominator will be the number of subjects in the RAS for each treatment group. The summary table will be sorted alphabetically for SOC, then by descending frequency of PT (for AVTX-002) within each SOC (then alphabetically for ties).

10.4 Prior and Concomitant Medications and Procedures

A prior medication or procedure is defined as having been received before the date of first study drug. A concomitant medication or procedure is defined as having been received on or after the date of the first dose of study drug (ie, either stops on/after the date of the first dose of study drug or is ongoing). Hence, a recorded medication may be both prior and concomitant.

Prior medications are captured from the screening visit, with the exception of ICS and LABA, which should also be recorded for the 3 months immediately prior to screening.

All prior and concomitant medications will be coded using the WHO-DD, version Sep 2021.

All prior and concomitant medications and procedures will be included in a subject listing, using the SAS. Any record/s where criteria for an asthma related event were met (see [Section 6.2.1](#)), will be flagged in the listing.

The number and percentage of subjects reporting prior and concomitant medications will be summarized by WHO-DD ATC Level 3 and preferred name, by treatment group, for the SAS. The same convention as detailed above for medical history (see [Section 10.3.1](#)) will be applied to the table summaries.

Prior/concomitant status (according to the definition provided at the start of this section) will be derived using the medication/procedure start and stop dates. For partial dates, see imputation rules in [Appendix 2 \(Table 4\)](#).

